Additionally, a more recent study conducted by Barbeito-Caamano et al concluded that the presence of a facemask did not have a significant change in physiologic parameters while during exercise⁵. Although there is evidentiary support that facemasks do not negatively affect oxygen status² and physiologic capacity, there is not strong evidence examining the relationship between ETCO2 and facemasks. The relationship between ETCO2 and facemasks is one of importance because mild decreases in oxygen have much less dangerous effects compared to the effects of rapid accumulations of carbon dioxide. Increases in end tidal carbon dioxide lead to confusion, acidosis and in severe cases, respiratory distress and failure. A study performed by Somers et al., in 1989 showed that hypercapnia has greater increases in blood pressure, minute ventilation and sympathetic nerve activity than hypoxia³.

In this newly proposed study, healthy volunteers will all wear the same type of three layer surgical mask. Their end tidal carbon dioxide will be measured while at rest without a mask, while resting with a mask and then after walking 100 meters in the mask. While previous studies have focused on changes in oxygen, there is a lack of research dedicated to analyzing end tidal carbon dioxide. This study will hope to show evidence supporting that there is no increase in end tidal carbon dioxide while wearing a mask.

METHODOLOGY

Study design

This study is a prospective, controlled study involving healthy adult volunteers all of whom are resident and faculty physicians, or other medical staff. There will be no financial compensation.

Intervention

After obtaining appropriate consent, subjects will have their end tidal carbon dioxide levels measured in three separate scenarios. Subjects will have their baseline end tidal carbon dioxide measured while at rest and without a mask. The second measurement will also occur at rest, but while subjects are wearing a mask. Lastly, end tidal carbon dioxide will be measured after each participant walks 100 meters, both with and without a surgical mask. These values will be compared during the data collection. In each of these scenarios, volunteers will also have their oxygen saturation measured.

Setting

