A maximum of 200 healthy adults will be enrolled at a Level 2 trauma center. Activities will be conducted inside of the hospital, where there is a large enough space to accommodate subjects walking the length of 100 meters. They will walk 100 meters twice, for a total of 200 meters.

Expected Start Date

Upon IRB approval.

Duration of Study

The study should take approximately six months to gather the data. An additional six months will be required to analyze the data and to prepare the study findings.

Study Subjects

The sample population will include Residents and staff members at Christus Spohn Shoreline. The maximum number of participants for this study will be 200.

Inclusion Criteria:

Healthy individuals between the ages of 18 and 75

Consent to participate in this study

Resident and ancillary staff

Exclusion Criteria:

Patients

Inability or refusal consent

Inability to walk the predetermined distance

History of lung disease

History of significant cardiac disease
People under the age of 18 and over the age of 75

Equipment/Supplies/Services

Supplies and services used for the study will consist of standard issued surgical masks, portable vital sign monitors of an undetermined brand, end tidal carbon dioxide measuring device better known as mask capnography, oxygen saturation measurement device, respiratory therapists.

Data Collection

Trained respiratory therapists will use the portable monitors to measure End tidal carbon dioxide values as well as oxygen saturation values. All values will be recorded into Excel.

Data Analysis

Statistical support will be provided by a member of the research team specializing in statistical analysis. De-identified ordinal data will be entered into an Excel spreadsheet and imported into a statistical analysis software program. Data will be analyzed by chi-square testing.

Data Management

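### Does naming only mask capnography, with no stated rule for a common sampling interface, undermine the masked-versus-unmasked ETCO2 comparison?

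*Protocol*

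**What the plan says.** The Equipment/Supplies/Services section of the Protocol lists standard surgical masks, "portable vital sign monitors of an undetermined brand", an "end tidal carbon dioxide measuring device better known as mask capnography", an oximeter and respiratory therapists. Data Collection adds only this: "Trained respiratory therapists will use the portable monitors to measure End tidal carbon dioxide values as well as oxygen saturation values".

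On the conditions, the Intervention section states: "Subjects will have their baseline end tidal carbon dioxide measured while at rest and without a mask". It continues: "The second measurement will also occur at rest, but while subjects are wearing a mask". For the walk, "end tidal carbon dioxide will be measured after each participant walks 100 meters, both with and without a surgical mask". The Background fixes the exposure: "healthy volunteers will all wear the same type of three layer surgical mask".

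No section describes how the capnography device is worn together with the surgical mask. None states that the interface and monitor stay the same across one volunteer's readings.

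**The concern.** The exposure is a mask, and the only ETCO2 tool named has the word mask in its label. Two readings of the text would cause trouble.

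- **Sampler on the face throughout.** The control reading would then not be bare-faced. The comparison becomes sampler alone against sampler plus surgical mask.
- **Sampler or monitor changes with mask status.** Any calibration or sampling offset between the two set-ups would be mixed with the mask effect. No later analysis could separate them.

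The offset could act in either direction, producing a false change or hiding a real rise. The second matters because the investigators hope to show that ETCO2 does not increase. The protocol standardises the surgical mask but leaves the monitor brand open and refers to monitors in the plural, so the measuring side looks loosely controlled.

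**Working it through.** The protocol gives no figure on this point to reproduce: no significance level, power, effect size or SD. The check is therefore of the text, followed by the algebra of a paired difference.

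**1. What the text supports**

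| Question | Evidence in the Protocol | Reading |
|---|---|---|
| What does the word mask mean in the control condition? | The walk sentence in Intervention specifies a surgical mask; the Background names one surgical mask type | The control is without the surgical mask |
| How many ETCO2 devices? | Equipment lists one, in the singular | One kind of device for the study |
| Does the device change with mask status? | No sentence says or implies it | Not supported |
| Why several monitors? | Up to 200 volunteers over about six months of data gathering | Unremarkable; says nothing about switching within a volunteer |

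**2. What an interface offset does**

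Let d be the true mask effect, and let o_m and o_u be the additive offsets of the set-up used for the masked and unmasked readings. Each volunteer's observed contrast has expectation

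d + b, where b = o_m − o_u.

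- Same interface and monitor for both readings: o_m = o_u, so b = 0 and the contrast estimates d.
- Different monitors for different volunteers, constant within each: b = 0 for every volunteer.
- Monitor changed within a volunteer for reasons unrelated to mask status: b averages zero. Noise is added, but no bias.
- Interface changed with mask status: b ≠ 0. Only this case biases the mask contrast.

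With a mask-type sampler worn throughout, the contrast is the added effect of the surgical mask. It departs from the effect on a bare face only if the two effects do not add, and the protocol gives nothing from which to size that.

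**3. Size in the one biasing case (illustration)**

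Assume d = 0 and a two-sided 5% paired t-test, with noncentrality (b/SD) × √n, where SD is that of the paired difference. The offsets and the test are assumptions (the protocol names chi-square). Only n = 200, the maximum, is from the protocol.

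| b/SD | n = 100: noncentrality | Rejection | n = 200: noncentrality | Rejection |
|---|---|---|---|---|
| 0 | 0 | 5% | 0 | 5% |
| 0.1 | 0.1 × 10 = 1.00 | 16.8% | 0.1 × 14.14 = 1.41 | 29.1% |
| 0.2 | 0.2 × 10 = 2.00 | 50.8% | 0.2 × 14.14 = 2.83 | 80.4% |

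These figures show that any systematic offset matters in a paired study of this size. They do not show that this protocol creates one.

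**4. How many readings are involved**

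Read as rest and walk, each with and without the mask, Intervention gives 2 × 2 = 4 readings per volunteer. That is at most 4 × 200 = 800, of which 2 × 200 = 400 are unmasked, with two like-for-like mask contrasts. The Background lists only three readings and no unmasked walk: at most 3 × 200 = 600, of which 200 are unmasked, and one such contrast. The algebra in step 2 is the same on either count.

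**5. Would prescribing another interface help?**

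The obvious substitute is a sampling line worn under the surgical mask. It passes the mask edge and could leak there, and it would do so only in masked readings. That is an offset tied to mask status, the one case in step 2 that biases the result. Nothing in the protocol shows that such a line would measure better than the listed device.

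**The case for a change.** The best case for a change is that the way a reading is physically taken belongs in a protocol and is not normally left to an analysis plan. ETCO2 is the only outcome in the objectives, a confounded contrast could not be repaired after data collection, and a sentence requiring the same set-up throughout costs almost nothing. A respiratory therapist reading the equipment list cannot be certain how the capnography device and the surgical mask are to be combined.

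Much of this stands. The text is silent, the label is awkward, and a bedside instruction naming the set-up and keeping it constant would be sensible practice. What does not stand is the step from silence to a flaw. The label may be loose wording for a monitor accessory. No passage points to switching by mask status, and a therapist taking paired readings from one person minutes apart has no evident reason to change equipment. The rejection rates depend wholly on a scenario that the text does not contain.

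**Conclusion.** No change to the plan is needed. The protocol leaves a measurement detail unwritten; it does not state anything wrong or contradict itself on this point. On the natural reading, one type of device is used throughout and the control is without the surgical mask. The within-person contrast then carries no interface bias (b = 0), and the false-positive rate stays at its nominal level, 5% in the illustration.

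This rests on two assumptions: that the same set-up is kept for a given volunteer's masked and unmasked readings, and that any offset it has simply adds. The singular device entry supports the first, though no sentence states it. The second cannot be tested from the document. If the set-up did change with mask status, the bias could be material, but neither its size nor its direction can be derived from the protocol. Replacing the listed device with a line under the mask offers no demonstrated gain and could itself introduce an offset confined to masked readings.

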Project Title

End Tidal CO2 and Masks: Is There a Correlation?

Co-Investigator Information

[name] MD
Department of Emergency Medicine
CHRISTUS Spohn Hospital Corpus Christi-Shoreline
[contact]/[contact]
[contact]

[name] MD
Department of Emergency Medicine
CHRISTUS Spohn Hospital Corpus Christi-Shoreline
[contact]
[contact]

[name]
Department of Emergency Medicine
CHRISTUS Spohn Hospital Corpus Christi-Shoreline
[contact]
[contact]

[name]
Shoreline Research Coordinator
CHRISTUS Spohn Hospital Corpus Christi-Shoreline
[contact]
[contact]

Principal Investigator

[name], DO
Emergency Medicine Resident
CHRISTUS Spohn Hospital Corpus Christi-Shoreline/Memorial
[contact]
[contact]

Objectives

The primary objective of this study is to evaluate if there are changes present with end tidal carbon dioxide while wearing a mask. A secondary objective is to assess possible changes in end tidal carbon dioxide while walking moderate distances while wearing a mask.

Research Question/Hypothesis

This aim of this study is to test the null hypothesis that end tidal carbon dioxide (ETCO2) will not change with mask wearing while at rest and while walking a moderate distance of 100 meters in a small sample of healthy adult volunteers.

Background to Research Questions

In light of the ongoing COVID-19 pandemic, wearing a mask has become a universal standard as an attempt to reduce the spread of COVID-19. As of 2020, more than half of all U.S. states have implemented a state wide mandated mask policy¹. There are many schools of thought regarding the benefits and risks of donning a mask to prevent the spread of COVID-19. There is an unproven theory among some that wearing a mask interferes with our natural respiratory function, causing hypoxia, altered mental status and other various health issues⁴. This dangerous perception has led some to believe wearing a mask is harmful, and encourages against wearing a mask in public. This theory, recently refuted by a study investigating oxygen levels while participants wore masks, performed in 2020 by Chan et al. encouraged increased compliance with wearing masks². Another study, preformed by Samannan et al, evaluated whether gas exchange abnormalities occurred with the use of surgical masks in subjects with and without lung function impairment⁶. The conclusions of the Samannan studied showed that regardless of lung function impairment, the presence of surgical masks did not impact gas exchange⁶.

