There will be minimal collection of protected health information including a name and signature. All data will be de-identified. Numerical data will be stored on a private, secure computer, owned by the principal investigator under fingerprint and password encryption. The signed consent forms will be kept in a locked file, stored in the locked office of [name], Research Coordinator. Her office is located on the 9th floor administrative office of CHRISTUS Spohn Hospital Corpus Christi-Shoreline. Only the Principal Investigator, Co-Investigators, and Statistician will have access to the data. All identifying information will be destroyed upon completion of the study.

Identified Risks/Ethical Considerations

Foreseeable risks include participant discomfort, shortness of breath and incidental exposure to COVID-19 as there will be measurements taken while a mask is not worn. There will be a session of counseling to discuss risks and complications of the participating in the study. There is a possible risk of breach of confidentiality. However, all effort will be made to protect the subjects' personal information. Identifying features of the patients will not be used, recorded, or presented in any abstract, manuscript, or oral presentation.

Benefits of Proposed Research to the Subjects and Others

Results of this study should disprove the theory that wearing a face mask interferes with natural respiratory function, causing hypoxia, altered mental status and other various health issues and instead provide evidence of the safety in compliance of wearing face masks in public to reduce exposure to the COVID-19 virus. This will benefit the general public by encouraging ongoing compliance with mask wearing policies.

Study Registration

This study will be registered with Clinicaltrials.gov after approval by the IRB and prior to participant enrollment.

References

1. <https://masks4all.co/what-states-require-masks/>

3. Somers, V. K., et al. "Contrasting Effects of Hypoxia and Hypercapnia on Ventilation and Sympathetic Activity in Humans." *Journal of Applied Physiology*, vol. 67, no. 5, 1989, pp. 2101–2106., doi:10.1152/jappl.1989.67.5.2101.

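### Chi-square testing of ordinal data, the only analysis named, does not fit paired numerical ETCO2 readings and cannot show how large a rise remains possible

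*Protocol*

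**What the plan says.** The hypothesis (Research Question/Hypothesis) is to "test the null hypothesis that end tidal carbon dioxide (ETCO2) will not change with mask wearing", at rest and after a 100-metre walk, "in a small sample of healthy adult volunteers". The Intervention section has each volunteer measured at rest without and then with a mask. It adds that "end tidal carbon dioxide will be measured after each participant walks 100 meters, both with and without a surgical mask".

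The Data Analysis section states "De-identified ordinal data will be entered into an Excel spreadsheet" and then "Data will be analyzed by chi-square testing". No other method appears, and no category, cut-point, paired method, effect estimate or interval is given. Data Management describes the same data differently: "Numerical data will be stored on a private, secure computer".

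The Background gives the hoped-for conclusion: "This study will hope to show evidence supporting that there is no increase in end tidal carbon dioxide while wearing a mask". On size, Study Subjects says only "The maximum number of participants for this study will be 200".

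**The concern.** Three things do not fit together: the question (a change within a person), the data (numerical monitor readings taken in pairs) and the test (chi-square on data labelled ordinal).

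- **Categories.** A chi-square test needs a table of counts. With no categories defined, cut-points would have to be chosen later, possibly with the data in view.
- **Pairing.** The natural reading is a Pearson chi-square, which treats masked and unmasked readings as coming from different people.
- **No estimate.** The test gives a p-value but no mean change and no confidence interval.

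The direction of the harm matters. With positive within-person correlation the test rejects too rarely, so the risk is a missed rise, not a false alarm. In a study that hopes to report no increase, that error favours the expected answer. A non-significant result would leave the reader unable to say how large a rise is still compatible with the data.

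**Working it through.** **No stated figure to reproduce.** The protocol gives no alpha, power, SD, correlation, effect size, unit or cut-point; 200 is a cap without a derivation. Everything numerical below is assumed: ETCO2 in mmHg, unmasked mean 38, SD 4 to 5, within-person correlation ρ from 0.5 to 0.8, two-sided 5%, n from 50 to 200.

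**1. Why Pearson chi-square is conservative here.** For two paired proportions, n × Var(p₁ − p₂) = p₁q₁ + p₂q₂ − 2cov. Pearson drops the covariance. For a median split of bivariate normal readings with no true effect, the correlation between the two yes/no values is φ = (2/π)·arcsin ρ, and the true standard error is √(1 − φ) times the one Pearson uses.

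- ρ = 0.5: φ = 0.333 and √0.667 = 0.816. Rejection needs |Z| > 1.96/0.816 = 2.40, so the true rate is about 1.6%.
- ρ = 0.8: φ = 0.590 and √0.410 = 0.640. Rejection needs |Z| > 1.96/0.640 = 3.06, so the true rate is about 0.2%.

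Simulation over all splits tried gave 0.2 to 2.7% against the nominal 5%.

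**2. Power of the paired t-test.** SD of the difference = SD·√(2(1 − ρ)); power ≈ Φ(δ√n / SD of difference − 1.96).

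- SD 4, ρ = 0.5, δ = 1, n = 200: SD of difference = 4; 1 × 14.14/4 = 3.54; Φ(1.58) = 94%.
- SD 5, ρ = 0.5, δ = 1, n = 200: SD of difference = 5; 14.14/5 = 2.83; Φ(0.87) = 81% (simulated: 80%).

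**3. Power of chi-square for the same rise.** With SD 4 and a cut at the unmasked mean of 38, the proportion above moves from 0.50 to Φ(1/4) = 0.599. The unpaired standard error at n = 200 is √(0.25/200 + 0.599 × 0.401/200) = 0.0495; 0.099/0.0495 ≈ 2.0, giving about 51%. Simulation on paired data gave 52%.

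**4. Wider comparison.** Integer-rounded paired readings, 6,000 replicates per cell. Ranges run over SD 4 and 5 and ρ of 0.5, 0.65 and 0.8. Central split means above 40 or above the pooled median.

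| True rise, n | Paired t | Chi-square, central split | Chi-square, above 45 | Chi-square, raw integers |
|---|---|---|---|---|
| 1 mmHg, 200 | 80 to >99% | 27–52% | 11–16% | 4–12% |
| 1 mmHg, 100 | 50–97% | 9–27% | 5–9% | 2–5% |
| 2 mmHg, 50 | 79 to >99% | 29–56% | 12–17% | 3–8% |
| 2 mmHg, 100 | 98 to >99% | 63–91% | 32–36% | 9–29% |
| 2 mmHg, 200 | >99% | 92 to >99% | 64–68% | 36–84% |
| 3 mmHg, 200 | ≥94% | ≥94% | ≥94% | ≥94% |

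**5. If a paired chi-square-type test was meant.** At 1 mmHg and n = 200, McNemar at above 40 has 46–82% power and the two-condition Friedman test 63% to >99%. McNemar still needs a cut-point, and neither gives a mean change with an interval.

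**6. What a paired analysis would report.** The 95% half-width is t × SD of difference/√n. At n = 200 it runs from about 1.97 × 2.53/14.14 = 0.35 (SD 4, ρ = 0.8) to 1.97 × 5/14.14 = 0.70 (SD 5, ρ = 0.5). At n = 50 it runs from about 0.7 to 1.4 mmHg.

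**The case against.** - **The figures are assumed.** This stands. Nothing in the protocol says a 1 mmHg rise matters, and the above-45 and raw-integer tables are illustrations, since the protocol defines no categories. The loss is negligible for 3 mmHg at 200 volunteers and small for 2 mmHg with a central split. The case must rest on the mismatch of test, data and design; the power figures show direction and possible size.
- **Cut-points, test variant and intervals can be left to an SAP.** True of each alone. But here the protocol itself fixes a test and a data type, so an SAP with a suitable paired analysis would contradict it.
- **A non-significant paired t-test would not show absence of an increase either.** Correct. Changing the test is not enough; the claim needs an interval read against a margin. The formal hypothesis is a conventional null of no change, so the margin is needed only because the Background aims to support no increase.
- **The walking contrast is not settled.** The Intervention section announces three scenarios but lists four readings, and the Background describes walking only in the mask. The Intervention wording and the two walks in the Setting section support an unmasked walking reading, but these places should be reconciled. The resting comparison is unaffected.
- **Other paired methods would also do.** Agreed: a signed-rank test or a mixed model would also cure the mismatch.

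**Conclusion.** The concern holds: the analysis is wrong as written and must be corrected before data are analysed. The undefined categories, the conflict between ordinal and numerical, and the lack of a mean change with an interval hold whatever values are assumed. Ignored pairing follows if the ordinary Pearson test is meant, which is the natural reading. The lost power depends on assumptions. Under those above it is severe for a 1 mmHg rise even at the cap of 200, substantial for 2 mmHg at 50 volunteers, and small or absent for 2 to 3 mmHg at 200 with a central split. Because the protocol speaks of a small sample and sets only a maximum, reaching 200 cannot be taken for granted. Even where power is adequate, a non-significant chi-square result could not support the conclusion the study hopes to reach.

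**What to change.** Replace the chi-square sentence in Data Analysis with wording such as:

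> *ETCO2 and SpO2 are analysed as continuous paired outcomes. The primary analysis is the within-person difference in ETCO2 (mask minus no mask) at rest, by paired t-test with 95% confidence interval. The mask minus no-mask difference after walking is analysed in the same way. A conclusion of no increase rests on the confidence interval compared with a margin stated before data collection, not on a non-significant test.*

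In the same section, describe the data as numerical and say that each participant's de-identified readings stay linked. Make the Background and Intervention sections agree on whether an unmasked walking reading is taken. The investigators choose and justify the margin. A signed-rank or mixed-model sensitivity analysis is optional and can go in the SAP.

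The cost is protocol wording and agreement on a margin before data collection. It adds no participants, and no measurements beyond those the Intervention section already lists.

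### The Benefits section promises to disprove harms of mask wearing that the outcomes, population, exposure and no-change hypothesis cannot disprove

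*Protocol*

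**What the plan says.** The section Benefits of Proposed Research to the Subjects and Others states: "Results of this study should disprove the theory that wearing a face mask interferes with natural respiratory function, causing hypoxia, altered mental status". The sentence goes on: "and other various health issues and instead provide evidence of the safety in compliance of wearing face masks in public". The next sentence names who gains: "This will benefit the general public by encouraging ongoing compliance with mask wearing policies".

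The rest of the protocol is narrower. Both objectives concern ETCO2. The Research Question/Hypothesis section sets a null of no change in ETCO2 at rest and over a 100 m walk, "in a small sample of healthy adult volunteers". The measurements are given under Data Collection: "Trained respiratory therapists will use the portable monitors to measure End tidal carbon dioxide values as well as oxygen saturation values". The Intervention section adds: "In each of these scenarios, volunteers will also have their oxygen saturation measured". The Background says that everyone wears the same type of three-layer surgical mask. Study Subjects caps enrolment at 200 residents and staff of one hospital, and the exclusions include "History of lung disease" and significant cardiac disease.

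**The concern.** The Benefits section fixes the conclusion before any data exist, and makes it wider than the study in four respects: the harms covered, the people studied, the exposure and the type of mask. It also asks a test of no change to do what such a test cannot do. A non-significant result says that an effect was not detected; it does not show that there is none.

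This matters for two reasons. The statement directly follows the risks section, which lists discomfort, shortness of breath and possible exposure to COVID-19 while unmasked. It is therefore what a review board weighs against those risks. And if the investigators later write their conclusion to match this section, they will claim a result that even a perfectly run study would not support.

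**Working it through.** The protocol gives no significance level, power, standard deviation, effect size or equivalence margin, and its sample size is only a maximum. There is thus no figure of its own to reproduce. The check sets the claim beside the design.

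| Element | Benefits section | Rest of the protocol | Match |
|---|---|---|---|
| Hypoxia | Disproved | Oxygen saturation measured in every scenario, but with no objective or hypothesis | Partial, short-term |
| Altered mental status | Disproved | Not measured; ETCO2 is measured, and the Background links raised CO2 to confusion | Indirect only |
| Other health issues | Disproved | Not measured | None |
| People | Safety in public, benefit to the general public | Healthy staff of one hospital, no lung or significant cardiac disease, at most 200 | Narrower |
| Exposure | Mask wearing, without limit | Masked rest of unstated length and one masked 100 m walk | Narrower |
| Mask | Any face mask | One type, three-layer surgical | Narrower |
| Inference | Disproof of an effect | Null of no change in ETCO2, with no margin stated | Does not follow |

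**Inference.** Under a null of no change, the data either reject it, which is evidence of a change, or fail to reject it. Failure to reject is compatible both with no change and with a change too small for the study to detect. To conclude that there is no important change, the protocol would need a margin and an interval lying inside it. It frames no such question.

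**Two illustrations of scale.** Neither measures the defect.

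1. *Length of the masked walk.* Time = distance / speed. The speed is an assumption, since the protocol gives none. At 0.8 m/s, 100 / 0.8 = 125 s. At 1.6 m/s, 100 / 1.6 = 62.5 s. Masked walking therefore lasts about one to two minutes.
2. *What a clean record would exclude.* Suppose that all 200 places are filled and no volunteer has a hypoxic reading, however defined. The exact one-sided 95% upper limit for the true frequency is 1 − 0.05^(1/200) = 0.0149, or 1.5%. At the 97.5% level it is 1 − 0.025^(1/200) = 0.0183, or 1.8%. With fewer volunteers the limits are higher. Even then they apply only to healthy staff under these conditions.

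**The case against.** The strongest reply is that this is a statement of hoped-for value. Eligibility, measurement and analysis do not depend on it, and the hypothesis section states the scope correctly. That is true, and it limits the weight of the point: no datum or test changes if the sentence stays. It does not make the sentence right. A stated benefit is meant to be relied on, and this one cannot be delivered.

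The second reply is that the theory at issue is a causal chain in which disturbed respiration leads to hypoxia and confusion. Both proposed mechanisms are measured, and evidence against a mechanism bears on the theory without a mental-status scale. This stands in part. ETCO2 does give indirect information on altered mental status, for these volunteers and conditions. It does not amount to disproof, and it does not reach the unspecified other health issues.

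A reader might infer more than the protocol supports:

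- *That the study says nothing about hypoxia.* It does say something: "volunteers will also have their oxygen saturation measured" in each scenario.
- *That the excluded patients are those in whom the question is most open.* The protocol gives no source for this. Its Background cites a study that included people with impaired lung function and found no effect of surgical masks on gas exchange. It is enough that this trial will not observe such people.
- *That every reading follows brief wear.* This is established for the walk only; the masked rest period has no stated length.
- *That the protocol claims its sample represents the general public.* It says that the public benefits through compliance. The extrapolation is implied by that phrase together with the claim of safety in public.

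**Conclusion.** The point holds as a mismatch between a stated benefit and the design. The claim of disproof is unsupported for all three named harms: hypoxia has partial evidence, altered mental status indirect evidence and other health issues none. Population, exposure and mask type are each narrower than the claim, and non-rejection of a no-change null would not deliver disproof in any case.

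The defect has no numerical size. The 1.5% limit and the walking time are illustrations that rest on an assumed full enrolment of 200 with no events and on assumed walking speeds. A reader should not take 1.5% as a property of the planned ETCO2 comparison.

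The conclusion rests on the protocol text alone. An analysis plan, if there is one, could add a margin or an outcome hierarchy. It could not supply outcomes that are not collected or people who are excluded. The matter deserves correction, but it does not threaten the data.

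**What to change.** Replace the sentence in the Benefits section with one such as: *The study will provide evidence on short-term change in ETCO2 and oxygen saturation in healthy adult hospital staff wearing a three-layer surgical mask, at rest and after a 100 m walk.* Delete the word disprove and the references to altered mental status and other health issues. Add that the results do not extend to people with lung or significant cardiac disease, to other mask types or to prolonged wear.

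Two consequential edits depend on how much is promised:

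- If hypoxia stays in the claim, list oxygen saturation, which is already measured, as a secondary outcome.
- If estimates with confidence intervals are promised, Data Analysis must change too. It now says that ordinal data will be compared by chi-square testing, which gives no interval for a change in ETCO2. A paired analysis of within-person change would bring the sections into agreement.

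The core change is wording only and needs no new data. The first optional edit touches the objectives and the second the stated analysis, so neither is purely editorial. The price is a stated benefit that looks less favourable.
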